**See the Schedule of Events (SOE) table below outlining all of the above procedures by visit.**

SHORT TITLE: ATX-PBPK-PD-Clinical Outcomes (U54)

Schedule of Events	Prescreen	Research Visit 1* θ	Intake with Study Physician ψ	Research Visit 2*	Research Visit 3*	6-Week Visit with Study Physician ψ	12-Week Visit with Study Physician ψ	18-Week Visit with Study Physician ψ	Research Visit 4*	2-week Post-Study Check
Time point	N/A	N/A	N/A	Start Med/Day 0	Day 0 + at least 2 weeks ε	Day 0 + 6 weeks and after RV3	6-Week Visit with Study Physician + 6 weeks	12-Week Visit with Study Physician + 6 weeks	After 18-Week Visit	After Research Visit 4
Visit Window	N/A	N/A	N/A	N/A	See note €	± 2 weeks	± 2 weeks	± 2 weeks	N/A	± 1 weeks
Type of Visit/Event	Phone	Phone/In Person	In person/telehealth	In Person	In Person	In person/telehealth	In person/telehealth	In person/telehealth	In Person	Phone
Potential Participant Identified	X									
Introduce the Study	X									
Schedule Research Visit 1	X									
Obtain Consent or Permission/Accent		X 								
Obtain participant continued assent (verbal)				X	X				X	
Document continued assent in research note				X	X				X	
Provide U54 Study Booklet		X								

SHORT TITLE: ATX-PBPK-PD-Clinical Outcomes (U54)

Schedule of Events	Prescreen	Research Visit 1* θ	Intake with Study Physician ψ	Research Visit 2*	Research Visit 3*	6-Week Visit with Study Physician ψ	12-Week Visit with Study Physician ψ	18-Week Visit with Study Physician ψ	Research Visit 4*	2-week Post-Study Check
Needlestick/Pill Swallowing Questions		X								
Explain and Begin Washout (if needed)		X								
Demographic Data		X								
Prior/Concomitant Meds		X		X	X	X	X	X	X	
Prior Medical History		X								
Vital Signs		X		X 	X 				X 	
Physical Exam		X	X	X	X	X	X	X	X	
Electrocardiogram		X							X	
Tanner Staging (optional)		X		X	X				X	
Pregnancy Test		X		X	X				X	
Safety Laboratory Tests (CBC w/diff; Base Met; LFTs; UA w/micro)		X		X	X				X	
Confirm ADHD Diagnosis			X							
Assess for Comorbidities			X			X	X	X		

SHORT TITLE: ATX-PBPK-PD-Clinical Outcomes (U54)

Confirm ATX appropriateness for participant			X							
Schedule of Events	Prescreen	Research Visit 1* θ	Intake with Study Physician ψ	Research Visit 2*	Research Visit 3*	6-Week Visit with Study Physician ψ	12-Week Visit with Study Physician ψ	18-Week Visit with Study Physician ψ	Research Visit 4*	2-week Post-Study Check
Interpret genotyping results				X 						
Assign study design				X 						
Determine medication dose				X 						
Pre-Visit Reminder Call				X 	X 	X 	X 	X 	X 	
Administer medication				X	X				X	
Dispense medication				X		X	X	X		
Dispense topical lidocaine (optional)				X	X				X	
Place IV				X	X				X	
Genotyping sample (blood)		X								
Pharmacokinetic sample (blood)				X	X				X	
Pharmacodynamic sample (blood)		X		X	X				X	
CYP2D6 Biomarker (urine)		X		X	X				X	

## SHORT TITLE: ATX-PBPK-PD-Clinical Outcomes (U54)

Pharmacokinetic sample (urine)				X	X				X	
Microbiome sample (saliva)		X		X	X				X	
Schedule of Events	Prescreen	Research Visit 1* θ	Intake with Study Physician ψ	Research Visit 2*	Research Visit 3*	6-Week Visit with Study Physician ψ	12-Week Visit with Study Physician ψ	18-Week Visit with Study Physician ψ	Research Visit 4*	2-week Post-Study Check
Sweat patches (sweat)				X	X				X	
Pupillometry during Posner's Cuing Task		X		X	X				X	
Dietary Survey Questionnaire									X	
Kiddie Schedule for Affective Disorders and Schizophrenia (KSADS)		X								
Kaufman Brief IQ Test (KBIT)		X								
Behavior Rating Inventory of Executive Function (BRIEF)		X							X	
Barkley Sluggish Cognitive Tempo Scale (SCT)		X							X	
Screen for Child Anxiety and Related Disorders (SCARED) – parent		X							X	

## SHORT TITLE: ATX-PBPK-PD-Clinical Outcomes (U54)

Screen for Child Anxiety and Related Disorders (SCARED) – child ( $\geq 8$ )		X							X	
Schedule of Events	Prescreen	Research Visit 1* θ	Intake with Study Physician ψ	Research Visit 2*	Research Visit 3*	6-Week Visit with Study Physician ψ	12-Week Visit with Study Physician ψ	18-Week Visit with Study Physician ψ	Research Visit 4*	2-week Post-Study Check
NICHQ Vanderbilt Assessment Scales – parent			X 			X	X	X		
NICHQ Vanderbilt Assessment Scales – teacher			X 			X	X	X		
Child Behavior Checklist – parent			X 						X	
Child Behavior Checklist – teacher			X 						X	
Strengths and Difficulties Questionnaire – parent			X 						X	
Strengths and Difficulties Questionnaire – teacher			X 						X	
Medication Side Effects – parent			X 			X	X	X		
Medication Side Effects – teacher			X 			X	X	X		

SHORT TITLE: ATX-PBPK-PD-Clinical Outcomes (U54)

School Intervention Questionnaire			X 					X		
Child Medical History Questionnaire			X 							
Schedule of Events	Prescreen	Research Visit 1 *	Intake with Study Physician ψ	Research Visit 2 *	Research Visit 3 *	6-Week Visit with Study Physician ψ	12-Week Visit with Study Physician ψ	18-Week Visit with Study Physician ψ	Research Visit 4 *	2-week Post-Study Check
Clinical Global Impression			X			X	X	X		
Adherence Check					X	X	X	X	X	X 
Adverse Events		X	X	X	X	X	X	X	X	X
Take Back U54 Study Booklet/Survey									X	

 Execution of permission/assent may occur via phone to allow participants to fill out psychometric questionnaires.

 Heart and blood pressure to take with each blood draw.

 These events occur prior to the visit for preparation.

 These phone calls occur in 2 parts.

 These questionnaires must be completed by the Intake Visit; however, they may be assigned at Research Visit 1 to allow participants ample time to complete.

 For participants recruited from Track 4, these questionnaires are assigned immediately after consent has been obtained.

 For participants who require a taper off medication.

\*These visits will occur in the Pediatric Clinical Research Unit (PCRU).

ψThese visits will occur at either the ADHD Clinic on College Boulevard or in the Developmental and Behavioral Sciences Clinic. If these visits are telehealth visits, all in-person procedures, such as obtaining vitals or a physical exam, may be omitted.

This visit can occur in two parts to minimize time of washout.

€The window for this visit is flexible and has been expanded from the previous versions of this protocol. This visit can occur anytime after the participant has been taking medication regularly for 2 weeks and up until prior to the 18-Week Visit with Study Physician.

○ Procedures to Reduce Risks

1. Medical Chart Review during Prescreen will be used to determine if a potential participant has any of the following:
  - a. Diagnosis or indication of underlying risk for cardiotoxicity, such as presentation of structural cardiac abnormalities, cardiomyopathy, or arrhythmias.
  - b. Diagnosis or indication of disease that may cause abnormal absorption or gastric emptying.
  - c. Previous history or indication of prior adverse drug reaction to atomoxetine
  - d. Concurrent therapy with drugs known to inhibit CYP2D6 or previous treatment with strong CYP2D6 inhibitors.
  - e. Concurrent therapy with other psychiatric/behavioral drugs
2. The two parts of Research Visit 1 may occur at separate times for participants who require a washout prior to beginning atomoxetine therapy. Research Visit 1 Part 1 includes a blood stick for genotyping purposes. Genotyping analysis, which takes approximately one week to complete and interpret, will be conducted while the participant is washing out. Were we to collect genotyping sample when the participant is at baseline, the participant could potentially be off of medication for ~ 2 weeks, while waiting for genotyping results such that ATX can be dosed in the participant using the iGO-PK model.
3. Needlestic comfort and pill-swallowing ability questions will be asked to reduce discomfort and anxiety associated with needlessticks and taking the study drug.
4. Baseline electrocardiogram during Research Visit 1 to assess presence of any underlying risks for cardiotoxicity prior to starting participant on ATX.
5. End of study electrocardiogram during Research Visit 4 to assess for any cardiac injury that may have occurred while the participant was taking ATX chronically.
6. Safety Labs – CBC with differential, hepatic function test, basic metabolic panel, and urinary analysis with microbiology will be conducted at Research Visit 1, Research Visit 2, Research Visit 3, and Research Visit 4.
7. Pregnancy Test will be conducted at Research Visit 1, Research Visit 2, Research Visit 3, and Research Visit 4 to ensure the subject is not pregnant.
8. Assessment of adverse events
9. For blood collection:

- a. Blood will be obtained either through needle stick (Research Visit 1) or through an indwelling venous catheter (Research Visit 2, Research Visit 3, and Research Visit 4).
  - b. With our study design, the maximal amount of blood drawn from any participant for clinical and research purposes for a research visit assigned Study Design 1 or 2 is 54 mL in a 72 hour period. This would mean that the lower limit for weight to complete study procedures is 11 – 15 kg. Our study population typically exceeds this weight range. However, given that there are multiple research visits where blood is drawn, for younger child and for those who are approximately 11- 15 kg, we will schedule research visits such that they are greater than 30 days apart.
  - c. For subjects who are less than 16.5 kg, the total amount of blood drawn from the subjects may exceed the 3 ml/kg/day limit, particularly if the individual is a CYP2D6 intermediate or poor metabolizer. The maximum amount of blood drawn within a 24 hour period is 48 mL.
  - d. With our study design, the maximal amount of blood drawn for a participant for clinical and research purposes for a research visit assigned Study Design 3 is 75ml in a 24 hour period. The majority of patients will not be enrolled under Study Design 3. The lower limit of weight to complete all possible blood draws for Study Design 3 is 15kg – 25kg (3- 5ml/kg = 75ml). Our study population typically exceeds this weight range. Additionally, participants in Study Design 3 may not be required to have all blood draws adding up to 75ml, as the number of draws depends on the timing of their dosing.
  - e. For Study Design 3 subjects who are less than 25 kg, research visits will be scheduled to not exceed predicted blood draw totals of 9.5ml/kg or more over an 8 week period.
10. Incidental findings which are discovered during the course of this study may be released to families in a letter at their request for the purposes of seeking further care (please refer to Appendix M).
11. During the COVID-19 pandemic, the research team will make every attempt to reduce the number of in-person procedures while providing ADHD care to the participant and achieving the aims of this research study.
12. The research team will adhere to all Children's Mercy Hospital and Children's Mercy Research Institute guidelines for reducing transmission of SARS-CoV-2 virus.
13. The research team will ensure that participants and their LARs have resources for reducing SARS-CoV-2 virus transmission from Children's Mercy Hospital and Children's Mercy Research Institute.

14. A Certificate of Confidentiality has been issued for this study by the National Institutes of Health which protects the privacy of research participants by prohibiting disclosure of identifiable and sensitive information. However, disclosure is permitted for the following scenarios:

- a. Required by Federal, State, or local laws (e.g., as required by the Federal Food, Drug, and Cosmetic Act, or state laws requiring the reporting of communicable diseases to State and local health departments), excluding instances of disclosure in any Federal, State, or local civil, criminal, administrative, legislative, or other proceeding;
- b. Necessary for the medical treatment of the individual to whom the information, document, or biospecimen pertains and made with the consent of such individual;
- c. Made with the consent of the individual to whom the information, document, or biospecimen pertains; or
- d. Made for the purposes of other scientific research that is in compliance with applicable Federal regulations governing the protection of human subjects in research.

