## 4.0 Study Endpoints and Rationale

### 4.1 Primary Study Endpoints

The primary aims of this study focus on characterizing the relationship between changes in pharmacodynamic markers and clinical outcome measures, when inter-subject variability in ATX pharmacokinetics has been minimized (Fig. 3). ATX pharmacodynamics will be measured using plasma DHPG and metabolomic data, pupillometry during attention tasks, and changes in blood pressure and heart rate. Clinical outcomes will be assessed by standardized ADHD measures used in a clinical setting, of which include: NICHQ Vanderbilt Assessment Scale (ADHD symptom rating scale); Strengths and Difficulties Questionnaire; Child Behavior Checklist; the School Intervention Questionnaire; Medication Side Effects; and Clinical Global Impression. Some of these questionnaires will also capture comorbidity information, such as Oppositional Defiant Disorder (ODD). We will also use the Kiddie Schedule for Affective Disorders and Schizophrenia for School-Age Children – Present and Lifetime Version (K-SADS-PL) or K-SADS-COMP (the computerized version of the K-SADS-PL) to diagnose ADHD and commonly associated comorbidities. The K-SADS-PL is a semi-structured interview that is extensively used in clinical psychology research to diagnose an extensive array of psychopathology based on the DSM-5. Given the length of this interview, common research practices are to select only the modules that are expected to be pertinent to the study participant (Black et al., 2012; Kariuki et al., 2018; Caudle et al., 2020). The K-SADS-PL modules selected for this research study are as follows: agoraphobia, separation anxiety disorder, social anxiety disorder/selective mutism, specific phobias, generalized anxiety, obsessive compulsive disorder, and post-traumatic stress disorder. The other research comorbidities or impairments that we will assess for and associated psychometric tests we will use are as follows: impairment in executive function using the Behavior Rating Inventory of Executive Function (BRIEF); anxiety using the Screen for Child Anxiety and Related Disorders (SCARED); intelligence quotient using the Kaufman Brief IQ Test (KBIT); and sluggish cognitive tempo using the Barkley Sluggish Cognitive Tempo Scale (SCT). Pharmacodynamic data will be obtained: baseline (Research Visit 1); when ATX is first initiated in a participant with the first dose (Research Visit 2); when the participant has taken the medication chronically and thus, expected to be at steady-state (Research Visit 3); and at the end of study when the dose has been optimized for the participant (Research Visit 4). Concurrent pharmacokinetic analysis will take place to ensure that ATX plasma and urine exposure variability has been minimized using methods described in a previous ATX pharmacokinetic study conducted at Children's Mercy Hospital (Brown et al., 2016). Additionally, we will measure ATX and metabolites in sweat as surrogate for fraction of drug unbound (Marchei et al., 2012; Marchei et al., 2013). The clinical ADHD questionnaires will be administered at the Intake Visit and at follow-up visits following initiation of atomoxetine treatment (6-weeks, 12-weeks, and

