## 11.0 Procedures Involved

### 11.1 Study Design Overview

This is a longitudinal exposure escalation study of atomoxetine in children with ADHD. This study simultaneously measures participants' pharmacokinetic and pharmacodynamic profiles after administration of a single-dose of ATX, approximately 2-8 weeks, and approximately 18 weeks of chronic use as well as the therapeutic efficacy/clinical response after chronic use. The study design is best illustrated by categorizing the chronological visits by phase as illustrated in Figure 4. The phases occur in the following order:

- 1) Prescreen
- 2) Enrollment
- 3) Screen
- 4) Intervention

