**Research Visit 3** – This visit is also referred to as pharmacokinetic study 2 (PK2) or steady state PK. This visit takes place in the PCRU and also includes procedures occurring in preparation of this visit, in addition to procedures after administration of medication when the participant is at steady-state. Steady-state is assumed to have been achieved once the participant has been taking atomoxetine routinely for two weeks. This visit may occur any time after the participant has been taking study drug routinely for 2 weeks and prior to the 18-Week Visit with Study Physician. If the participant is prescribed non-Q12-hour twice daily dosing at this time, the study team will notify participant and/or family prior to visit, and the participant will be switched to Study Design 3 for this research visit. Compliance will be documented by checking the capsule count against the medication calendar and documented in corresponding CRFs. Additionally, study personnel will reach out participants and/or their families ~1 week

prior to remind them that all medications need to be taken in the week prior to Research Visit 3. Study personnel will call prior to Research Visit 3 to ensure that participants have been compliant for a week.

6-Week Visit with Study Physician – The participant and family meet with a study physician approximately 6 weeks after ATX therapy was initiated. A ± 2-week window is allowed for ease of scheduling and to ensure Research Visit 3 occurs prior to the visit. Prior to this visit, questionnaires will be sent out via CHADIS to parents and teachers to assess participant's behavior. During this visit, safety, efficacy, and side effects will al be assessed and dose adjustments will be made accordingly. Dose adjustments may be outside research and visits with study physicians as needed.

12-Week Visit with Study Physician – The participant and family meet with a study physician approximately 6 weeks after the 6-Week Visit with Study Physician. A ± 2-week window is allowed for ease of scheduling. Prior to this visit, questionnaires will be sent out via CHADIS to parents and teachers to assess participant's behavior. During this visit, safety, efficacy, and side effects will be assessed and dose adjustments will be made accordingly. Dose adjustments may be outside research and visits with study physicians as needed.

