18-Week Visit with Study Physician – The participant and family meet with a study physician approximately 6 weeks after the 12-Week Visit with Study Physician. A ± 2-week window is allowed for ease of scheduling. Prior to this visit, questionnaires will be sent out via CHADIS to parents and teachers to assess participant's behavior. During this visit, safety, efficacy, and side effects will be assessed and dose adjustments will be made accordingly. In addition, baseline questionnaires will be re-administered to gauge symptom and impairment changes post-treatment initiation. Dose adjustments may be outside research and visits with study physicians as needed.

Research Visit 4 – This visit is also referred to as pharmacokinetic study 3 (PK3) or end of study PK. This vist occurs after the 18-Week Visit with Study Physician. This visit takes place in the PCRU and consists of the same procedures as Research Visit 3. Determination of Study Design will be confirmed prior to visit, as some participants may require switching to a different study design if frequency of dosing has changed. During this visit, baseline psychometric measures will be re-administered to measure change post-treatment initiation. An end of study EKG will be obtained, and a Dietary Survey Questionnaire will be administered.

- Description of Research Procedures

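### Research Visit 3 has two incompatible timing rules; under the wider one, response-driven dose changes can confound unadjusted DHPG and pupil comparisons that use its data

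*Combined protocol and SAP*

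**What the plan says.** **Early timing.** In Section 11.1, the 6-Week Visit paragraph states: "A ± 2-week window is allowed for ease of scheduling and to ensure Research Visit 3 occurs prior to the visit". The Schedule of Events gives the time point of the 6-week visit as "Day 0 + 6 weeks and after RV3". The Study Design Overview in Section 11.1 describes profiles after a single dose, "approximately 2-8 weeks, and approximately 18 weeks of chronic use".

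**Wide timing.** The RV3 paragraph of Section 11.1 allows the visit any time after the child has been taking study drug "routinely for 2 weeks and prior to the 18-Week Visit with Study Physician". The Schedule of Events footnote allows it "up until prior to the 18-Week Visit with Study Physician", and adds that the window was widened from previous protocol versions.

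**Dosing around RV3.** Section 5.1 starts from a predicted Cmax,ss of 400 ng/mL. It allows titration to 600 or 800 ng/mL according to response, reduction below 400 for toxicity, and a slow approach to 400. Section 11.1 provides for dose adjustment at the 6-, 12- and 18-week visits and between visits. Section 11.2 also allows it before the 6-week visit.

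**Analysis.** Section 20.1 compares percent decrease in DHPG, overall DHPG change, pupil-diameter change, Imax and IC50 between responders and non-responders. Section 20.2 names baseline and maximal change in DHPG. Neither section says which visit supplies these values. The only confounder Section 20.1 names for the marker-response analyses is adherence.

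**The concern.** Section 3.2 argues that drug-target effects cannot be studied unless variation in exposure is first minimized. Section 4.1 accordingly distinguishes RV3 (steady state) from RV4 (dose optimized). If RV3 can follow titration, the two visits overlap in meaning.

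The specific risk is confounding rather than noise. Dose is raised when response is poor, and Section 4.1 says atomoxetine lowers plasma DHPG. Children heading for non-response may therefore be sampled at RV3 on a higher exposure target and show a larger DHPG fall because of dose. RV3 timing need not itself depend on response for this to happen. It is enough that RV3 falls after titration steps that did depend on it. An unadjusted two-sample test would then mix the marker difference of interest with a dose difference and a time-on-drug difference.

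**Working it through.** **1. Reproduce the plan's own range.** Early rule: the lower bound is 2 weeks of dosing, and the upper bound is the 6-week visit at its latest, 6 + 2 = 8 weeks. This gives 2-8 weeks, the figure in the Study Design Overview. Only the early rule reproduces it.

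**2. Apply the wide rule.** The upper bound is the 18-week visit. Section 11.1 chains this as "approximately 6 weeks after the 12-Week Visit with Study Physician", with the 12-week visit 6 weeks after the 6-week visit and ±2 weeks at each step.
- Nominal: 6 + 6 + 6 = 18 weeks.
- Earliest: 4 + 4 + 4 = 12 weeks. Latest: 8 + 8 + 8 = 24 weeks.

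| | Early rule | Wide rule |
|---|---|---|
| Nominal upper bound (latest) | week 6 (8) | week 18 (24) |
| Scheduled adjustment visits before RV3 | 0 | 0, 1 or 2 |

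**3. Permitted exposure.** Upward titration spans 800/400 = 2.0 in target Cmax,ss. Targets below 400 are also allowed. This is the range the text permits, not an observed difference.

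**4. Which analyses are exposed.** The indirect-response and Emax models in Section 20.1 relate DHPG to plasma atomoxetine concentration, and Imax and IC50 come from such models. These condition on exposure. The two-sample tests of percent, maximal or overall DHPG change and of pupil change do not.

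**5. Check of the stated power.** Inputs from Section 20.2: 30% responders, one-sided α = 0.05. Noncentral t with ncp = d / √(1/n₁ + 1/n₂).
- N = 120 (36 and 84), d = 0.5: ncp = 0.5/0.199 = 2.51, power 80.3%. The plan's figure is reproduced.
- N = 96 (29 and 67), d = 0.6: ncp = 0.6/0.222 = 2.70, power 85.0%. The difference detectable at 80% is 0.557 SD, consistent with the plan's 0.6 after rounding.

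Neither figure depends on the RV3 window.

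**6. Illustration with assumed values.** The documents give neither the DHPG shift from titration nor how many children have a late RV3. Assume titration enlarges the DHPG fall by δ SD, that responders truly have the larger fall by 0.6 SD, and that non-responders are measured after titration more often by a proportion Δf. Bias = δ × Δf, and the apparent difference is 0.6 − δ × Δf. One-sided power at N = 96, with the SD held at 1:

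| δ (SD) | Δf = 0.2 | Δf = 0.4 | Δf = 0.6 |
|---|---|---|---|
| 0.25 | 0.55 SD, 79.2% | 0.50 SD, 72.2% | 0.45 SD, 64.2% |
| 0.5 | 0.50 SD, 72.2% | 0.40 SD, 55.6% | 0.30 SD, 38.0% |
| 1.0 | 0.40 SD, 55.6% | 0.20 SD, 22.6% | 0.00 SD, 5.0% |

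If instead half of each group is measured after titration (no differential), the SD becomes √(1 + 0.25δ²) = 1.008, 1.031 or 1.118, and power at 0.6 SD is 84.5%, 83.0% or 77.4%. The differential part matters more than the added noise.

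**The case against.** **The wide window looks deliberate.** The footnote says it was expanded, so the early phrases may simply be text that was not updated. That is plausible, but both rules stand in current text, within one section, and site staff cannot follow both.

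**The contradiction does not by itself create mixed exposures.** A reader might infer that moving RV3 back before the 6-week visit would give a uniform 400 ng/mL visit. The documents do not support that. Dose may change before the 6-week visit, including for lack of efficacy, and physicians may approach 400 slowly. An early RV3 would reduce the mixing, not remove it.

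**Exposure is partly handled.** PK is sampled alongside PD at RV3, Cmax,ss and AUC are derived, and the main DHPG model is concentration-based. The study is also openly an exposure-escalation design. All of this stands, and it confines the concern to the group tests that do not use concentration.

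**No main RV3 comparison is defined.** This is also correct. The concern applies when those tests draw on RV3 data, and the plan leaves that open because it names no visit.

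**Restricting the main analysis to children still on the starting target would bring its own bias.** Poor responders are titrated up and intolerant children down, so that subset is selected on response and tolerability. The objection is sound and limits the restriction to a sensitivity role.

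**Conclusion.** The timing rules for RV3 conflict in current text and need to be reconciled. Under the wide rule, the nominal upper bound moves from week 6 to week 18, and up to two scheduled response-driven adjustments can precede the visit. This adds to mixing already possible through earlier dose changes and slow titration. The tests of DHPG and pupil change that do not condition on concentration can be confounded when they use RV3 data; the concentration-based models are less exposed.

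The two-fold target ratio might be read as the size of the problem. It is only a permitted extreme. The documents allow the mixing but do not show that it occurred, and the bias cannot be computed from them. The illustrative losses rest wholly on assumed δ and Δf and on the assumed direction of effect. No stated sample size or power figure needs to change on this account. The point merits correction because a bias in a central comparison can be reduced with data already being collected.

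**What to change.** - Reconcile the Study Design Overview, the RV3 and 6-Week Visit paragraphs of Section 11.1, and the Schedule of Events time point and footnote to one RV3 timing rule, whichever the sponsor intends.
- In Sections 20.1 and 20.2, name the visit that supplies each DHPG and pupil comparison.
- For comparisons using RV3 data, adjust for observed exposure at that visit (Cmax,ss or AUC) and days on drug, alongside adherence. Section 20.1 takes AUC to 12 or 24 hours depending on study design, so if AUC is chosen it needs a common interval.
- Report the comparison in children still on their starting target as a sensitivity analysis only, and say that the subset is selected on response and tolerability.

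Cost: wording in Sections 11.1, 11.2 and 20, a few extra covariates and a little more analysis work. Exposure is already derived, and days on drug follow from Day 0 and the visit date. No new visit or sample is needed.

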  - i. These tests may be omitted if these data were collected in the week prior, at the discretion of the study coordinator, the physician performing the physical exam, or any person designated in the delegation of authority log.
- g. Collect urine for urinalysis with microbiology.
- h. Perform urinary pregnancy test on female subjects.
- i. Collect baseline urine sample (~10 mL) for predose urine sample and CYP2D6 biomarker analysis.
- j. Confirm prior to dosing that participant is:
  - i. Healthy enough to continue Research Visit 2 (sign off on safety labs and physical exam sheet by physician).
  - ii. Not pregnant, females only (urine pregnancy test).
- k. Place two sweat patches on the participants back. The sweat patch is 15.4 cm^2 in size and consists of a cellulose blotter paper collection pad

(PharmChek®, PharmaChem Laboratories, Menlo Park, CA). Prior to patch placement, clean the area of skin to which the patch will be applied with rubbing alcohol.

- i. Collect pre-dose blood, blood pressure, and heart rate prior to dosing medication.
- m. Administer dose of atomoxetine according to prescription.
- n. Collect 3 mL of blood, blood pressure, and heart rate at the following time points after dose administration:
  - i. Timeframe:
    - i. Study Design 1: 0.5, 0.75, 1, 1.5, 2, 3, 4, 6, 8, 10, 12, 16, 20, 24, 48, and 72 hours.
    - ii. Study Design 2: 0.5, 0.75, 1, 1.5, 2, 3, 4, 6, 8, 10, and 12 hours.
    - iii. A window of  $\pm$  5 minutes is acceptable for blood draws at time points 0.5 – 2 hours.
    - iv. A window of  $\pm$  15 minutes is acceptable for blood draws at all other time points.
  - ii. Collection Instructions: 2 mL of blood will be collected in a EDTA tube and 1 mL of blood will be collected in a serum gel separator tube.
  - iii. Processing: Within an hour of collecting sample, plasma and serum will be separated by centrifugation at 4°C (1000 – 2000 g x 10 min), aspirated manually, and transferred to polypropylene cryovials for storage at -70°C until analysis.
- o. Collect and pool urine starting after dose administration.

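### The 11–15 kg weight limit for blood draws in section 11.3, item 9b, does not follow from its own 54 mL and disagrees with item 9c, so a narrow band of Study Design 1 children has no weight-based trigger for wider visit spacing

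*Combined protocol and SAP*

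**What the plan says.** All the figures are in section 11.3 (Procedures to Reduce Risks), item 9.

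- **Item 9b** puts the maximum volume "for a research visit assigned Study Design 1 or 2 is 54 mL in a 72 hour period" and infers from it: "This would mean that the lower limit for weight to complete study procedures is 11 – 15 kg". It adds a precaution on the interval between visits: "for younger child and for those who are approximately 11- 15 kg, we will schedule research visits such that they are greater than 30 days". It states no mL/kg limit.
- **Item 9c** says: "For subjects who are less than 16.5 kg, the total amount of blood drawn from the subjects may exceed the 3 ml/kg/day limit", in particular for CYP2D6 intermediate or poor metabolizers. It continues: "The maximum amount of blood drawn within a 24 hour period is 48 mL". No precaution follows.
- **Item 9d**, for Study Design 3 with 75 mL in 24 hours, shows its basis: "The lower limit of weight to complete all possible blood draws for Study Design 3 is 15kg – 25kg (3- 5ml/kg = 75ml".
- **Item 9e** then sets a cumulative safeguard for Study Design 3 children below 25 kg, the upper end of the range in 9d.

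Items 9b and 9d both say that the study population typically exceeds these weights. Section 6.1 admits children from age 6, and neither the inclusion nor the exclusion criteria set a minimum weight. Section 11.1 and the Schedule of Events allow Research Visit 3 at any time from two weeks of regular dosing until before the 18-week visit.

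**The concern.** A weight threshold that triggers a pediatric blood-volume precaution should follow from the stated volume and the stated limit. In item 9b the upper end does not. Item 9c then places the point at which a daily limit may be exceeded above the weight that 9b names for wider spacing. Study staff reading the two items together cannot tell whether a child just above 15 kg gets the precaution. Item 9b mentions younger children as well, but gives no age or weight by which to apply that phrase consistently.

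At stake is whether a small Study Design 1 child could have two large-volume visits close together when the protocol meant them to be spread out.

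**Working it through.** **Inputs.** 54 mL in 72 hours (9b); 48 mL in 24 hours and 3 mL/kg/day (9c); 75 mL in 24 hours and 3–5 mL/kg (9d); and the sampling times in section 11.2. The formula throughout is weight limit = volume ÷ (mL per kg).

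**1. Do the stated volumes agree with the sampling schedule?** At Research Visit 2 the instruction is "Collect 3 mL of blood, blood pressure, and heart rate at the following time points after dose administration", and the times are "Study Design 1: 0.5, 0.75, 1, 1.5, 2, 3, 4, 6, 8, 10, 12, 16, 20, 24, 48, and 72 hours". The documents give no volume for the pre-dose research sample or the safety laboratory tests. I assume 3 mL for each.

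| Visit | Draws (pre-dose + timed) | × 3 mL | + 3 mL safety labs | Stated |
|---|---|---|---|---|
| Design 1, Visit 2, 72 h | 1 + 16 = 17 | 51 | 54 | 54 (9b) |
| Design 1, first 24 h of Visit 2, or Visit 3 or 4 | 1 + 14 = 15 | 45 | 48 | 48 (9c) |
| Design 2, 12 h | 1 + 11 = 12 | 36 | 39 | none |
| Design 3, maximum | 12 + 12 = 24 | 72 | 75 | 75 (9d) |

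The volumes are consistent. The 54 mL arises only at Research Visit 2 in Study Design 1.

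**2. Reproduce the range in 9d.** 75/5 = 15 kg and 75/3 = 25 kg, an exact match.

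**3. Apply the same basis to 9b.** 54/5 = 10.8 kg, which matches the printed 11. 54/3 = 18 kg, which does not match the printed 15. At 15 kg, 54/15 = 3.6 mL/kg.

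**4. Could another volume explain 11–15 kg?** A lower end of 11 kg at 5 mL/kg needs 11 × 5 = 55 mL, and an upper end of 15 kg at 3 mL/kg needs 15 × 3 = 45 mL. Rounding each weight to the nearest kilogram allows 52.5–57.5 mL for the first and 43.5–46.5 mL for the second. The intervals do not overlap, so no single volume yields both ends. The 45 mL equals the 24-hour timed draws without safety labs, but that is not a stated maximum, and 45/5 would make the lower end 9 kg.

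**5. Check 9c against itself.** 48/3 = 16.0 kg. The printed 16.5 kg corresponds to 16.5 × 3 = 49.5 mL. At 16.5 kg, 48 mL is 2.9 mL/kg; at 15 kg it is 3.2 mL/kg.

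**6. The Study Design 1 band above 15 kg with no weight-based trigger, by basis.**

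| Basis | Upper weight | Band |
|---|---|---|
| 3 mL/kg/day on 48 mL | 16.0 kg | about 15–16 kg |
| Item 9c as printed | 16.5 kg | about 15–16.5 kg |
| 3 mL/kg on the whole 72-hour visit (54 mL) | 18 kg | about 15–18 kg |

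**7. Study Design 2.** 39/3 = 13 kg, so a Design 2 child above 15 kg is below 3 mL/kg.

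**The case against.** The strongest reply has four parts.

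- **The mL/kg basis is borrowed.** The 3–5 mL/kg range is written only for Study Design 3. Item 9b states no limit, and its 54 mL is a 72-hour total. The only limit in the items for Designs 1 and 2 is 9c's, and it is per day. This stands. A reader might infer that all children of 15–18 kg exceed a stated limit. The documents support that only if 3 mL/kg is taken to cap the whole 72-hour visit, which they do not say.
- **The precaution is wider than 11–15 kg.** Item 9b also covers younger children and says its weights are approximate. A reader might infer that a small 6- or 7-year-old just above 15 kg gets no spacing at all, but the text does not support that: such a child could well count as younger. What remains is that the term is undefined, so coverage depends on who reads it.
- **Not every design is involved, and items 9c and 9d need not match 9b.** Design 2 volumes are too small to matter in this weight range, and 9d concerns a different volume and should give a different range. Both points are right. The conflict is between 9b and 9c. The half-kilogram discrepancy inside 9c errs on the cautious side and is minor by itself.
- **No cumulative breach is shown.** A 15.5 kg Design 1 child would give 54 + 48 = 102 mL over Research Visits 2 and 3, or 102/15.5 = 6.6 mL/kg, possibly little more than two weeks apart. A reader might take this as a violation, but no cumulative limit is stated for Design 1. Item 9e's 9.5 mL/kg over 8 weeks is for Design 3 only, and 6.6 is below it.

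None of this makes 9b's upper end reproducible or brings 9b and 9c into agreement.

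**Conclusion.** The point holds as an internal inconsistency in a safety threshold, limited to Study Design 1. The printed upper end of 15 kg is 3 kg below what 54 mL gives on the basis used in 9d. On any of the three bases, some children above 15 kg are over 3 mL/kg, or flagged by 9c, with no weight-based trigger for spacing. The band is 1 to 1.5 kg wide on the per-day readings and 3 kg wide on the per-visit reading.

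The threshold arithmetic uses only the stated 54, 48 and 75 mL. The assumption of 3 mL each for the pre-dose sample and safety labs enters only the match to the sampling schedule and the 39 mL for Design 2. Few children are likely to be affected, since the protocol says that its population typically exceeds these weights. The correction is still worth making, because the text governs a precaution for the smallest participants and no minimum weight in section 6.1 limits exposure. The documents do not show that any stated cumulative limit is exceeded, and they do not settle which limit the sponsor intended.

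**What to change.** Recompute and reconcile items 9b, 9c and 9d in section 11.3. State one mL/kg basis and one time base (per day or per 72-hour visit), and show the division for each design as 9d already does. Give 54 mL as the Research Visit 2 maximum for Study Design 1, and show the smaller Design 2 volume separately. Define the younger group in 9b by age or weight. Make the children covered by the spacing precaution agree with the reconciled threshold, and say in 9c whether any action applies to the children it flags. Which limit and which spacing rule apply is for the sponsor to decide.

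The cost is a text correction in one section. If the reconciled group turns out wider, Research Visit 3 may fall later for a few small children, and the existing flexible window for that visit leaves room for this.
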